### **PROTOCOL TEMPLATE INSTRUCTIONS HRP-503**

- *These instructions accompany the MSSM “Template Protocol” document and are intended to assist you in developing a human research protocol.*
- *Using the MSSM “Template Protocol” document, prepare a document with the following sections.*
- *Note that, depending on the nature of your research, certain questions, directions, or entire sections below may not be applicable. Provide information if and when applicable, and in cases where an entire section is not applicable, indicate this by marking the section “N/A”. Do not delete any sections.*
- ***For any items below that are already described in the sponsor’s protocol, the investigator’s protocol, the grant application, or other source documents, you may simply reference the title and page numbers of these documents in the sections below, rather than cutting and pasting into this document. Do NOT refer to any derived documents, such as the Sample Consent document, or other internal documents required with the submission.***
- *When you write a protocol, keep an electronic copy. You will need to modify this copy when making changes.*

The incidence of hepatocellular carcinoma (HCC) has recently increased in the United States. Although imaging plays a major role in HCC screening and staging, the possibility of predicting HCC tumor grade, aggressiveness, angiogenesis and hypoxia with imaging are unmet needs. In addition, new antiangiogenic drugs now available to treat advanced HCC necessitate the use of new imaging criteria beyond size. In this proposal, we would like to develop and validate quantitative MRI and PET/MRI methods as markers of histopathologic features of HCC, and to predict and assess early response of HCC to systemic therapy with sorafenib. We also would like to develop quality control tools to improve the quality and decrease variability of quantitative MRI and PET/MRI metrics. These techniques combined could represent non invasive correlates of histologic findings in HCC, could enable individualized therapy, and provide prognosis in patients with HCC.

#### **1) Objectives**

- a) Test and validate a quantitative multiparametric scoring system combining measurements of MR diffusion, perfusion, stiffness and hypoxia against histopathologic measures of tumor grade, cellularity, aggressiveness, angiogenesis, hypoxia and microvascular invasion in HCC.
- b) Assess the role of combined FDG-PET and MRI for assessment of HCC tumor characteristics in a pilot study in a small subset of patients with HCC.
- c) Compare the diagnostic performance of MRI to ultrasound elastography (ARFI: Acoustic Radiation Force Impulse) to measure liver and HCC stiffness.

	Protocol Name:	Evaluation of HCC Response to Systemic Therapy with Quantitative MRI
	Principal Investigator:	[name]
	Primary Contact Name/Contact Info:	[name] [contact] [contact]
	Date Revised:	6/30/2017
	Study Number:	GCO12-0214

- d) Correlate advanced imaging findings with gene expression profiles measured in resected or biopsy tumor samples.
- e) Assess the predictive value of multiparametric MRI in patients with advanced HCC treated with systemic therapy and/or Yttrium 90 radioembolization.

Hypothesis: There is a negative correlation between diffusion metrics (D: true diffusion coefficient and ADC) and tumor grade/cellularity and aggressiveness; a positive correlation between PF (perfusion fraction) measured with IVIM, arterial fraction (ART) measured with DCE-MRI and each of MVD (microvessel density) and VEGF expression; and a positive correlation between  $\Delta R2^*$  (measured with BOLD) and each of MVD and HIF 1- $\alpha$  (hypoxia inducible factor 1-alpha) expression.

Hypothesis: FDG-PET parameters correlate with HCC tumor grade, and may add information to MRI metrics.

Hypothesis: There is a correlation between quantitative MRI and PET and certain gene expression profiles in tumors.

*Hypothesis: Quantitative MR parameters may enable prediction and assessment of response to systemic therapy and/or Y90 radioembolization.*

## 2) Background

The incidence of hepatocellular carcinoma (HCC) has recently increased in the US mostly due to an increase in chronic hepatitis C infection. Angiogenesis is critical for the growth and metastatic progression of HCC, and involves different molecular pathways including VEGF (vascular endothelial growth factor) which is released following a hypoxic stimulus, inducing hyperpermeability of tumor vessels. The arterial vascular profile of HCC has provided the basis for the use of transarterial chemoembolization (TACE) as an effective therapy to cause tumor necrosis. Imaging plays an essential role in HCC screening, diagnosis and staging. However, the assessment of HCC tumor grade and aggressiveness, and the prediction of response of HCC to TACE using imaging criteria are not established. With the development of new antiangiogenic drugs recently approved in advanced human HCC, such as sorafenib, imaging methods to predict and assess therapeutic response beyond changes in size become critical. It has been recently suggested that assessing the degree of residual tumor enhancement on dynamic CT or MRI using modified RECIST (mRECIST) criteria in HCC treated with TACE or systemic therapy is more appropriate than the use of conventional RECIST criteria (which are based on size only).

Recently, functional MRI methods have shown promising results for evaluation of tumor cellularity and grade, angiogenesis and hypoxia. Apparent diffusion coefficient (ADC) measured with diffusion-weighted imaging (DWI) has been correlated with tumor cellularity in brain, prostate and breast tumors and with HCC tumor grade, and has been used for assessment of response of HCC to TACE. BOLD (blood oxygen level dependent) MRI experiments have demonstrated a decrease in  $R2^*$  after oxygen or

	Protocol Name:	Evaluation of HCC Response to Systemic Therapy with Quantitative MRI
	Principal Investigator:	[name]
	Primary Contact Name/Contact Info:	[name] [contact] [contact]
	Date Revised:	6/30/2017
	Study Number:	GCO12-0214

carbogen challenge, thus providing a simple noninvasive tool to evaluate hypoxic tumors such as HCC. Dynamic contrast-enhanced MRI (DCE-MRI) has been correlated with tumor microvessel density (MVD) and VEGF expression and has been used to follow antiangiogenic treatments in liver metastases. Our recent data suggest that tumor ADC correlates with HCC grade and can be used to predict HCC response to TACE; and that tumor perfusion (measured with DCE-MRI) and oxygen uptake (measured with BOLD) are promising non invasive markers of HCC angiogenesis and hypoxia. In addition, recent work by other investigators and our group showed the possibility of separating diffusion and perfusion in the liver using the IVIM (intravoxel incoherent motion) model. Despite these promising results, data correlating DWI (without or with IVIM), DCE-MRI and BOLD with histopathology in human HCC remain extremely limited. Moreover, validated imaging methods to predict and assess early HCC response to new targeted agents such as sorafenib are lacking.

Intratumoral hypoxia has been shown to correlate with tumor invasiveness, progression, metastasis and radioresistance. Given that HCC is a hypervascular tumor, anti-angiogenic therapy offers a promising approach, and potent experimental antiangiogenic drugs such as angiostatin, endostatin, vasostatin and TNP-470 are effective in treating experimental models of HCC. Sorafenib (Nexavar, Bayer HealthCare–Onyx Pharmaceuticals) is an oral multikinase inhibitor with anti-angiogenic, pro-apoptotic and Raf kinase inhibitory activity, which has shown small increase in survival in the SHARP trial compared to placebo, and is currently FDA approved for use in advanced human HCC.

There is also recent interest in immunotherapy drugs in HCC, with a trial of nivolumab (Opdivo) opening soon at Mount Sinai. Yttrium 90 radioembolization is emerging as an efficient locoregional therapy in HCC, and is now often performed at Mount Sinai.

ADC measured with DWI has been shown to correlate negatively with tumor cellularity in brain, breast and prostate tumors. Recent data suggest a correlation between tumor ADC and HCC grade. ADC is also increasingly applied to evaluate tumor response to local or systemic therapy in liver tumors. Pre-clinical and clinical studies have shown that effective tumor treatment results in a rise in tumor ADC, which can occur prior to any measurable change in tumor size. Following the increase in ADC with treatment, the ADC will subsequently fall, related to tumor repopulation, fibrosis or tissue remodeling and decreased perfusion. There are several reports on the use of ADC to evaluate HCC response to chemo- or radioembolization. These studies demonstrated measurable differences before and after treatment. There is very limited published data on the use of DWI after treatment of HCC with sorafenib, and no data on the use of DWI for predicting response of HCC to therapy.

BOLD MRI can detect oxygenation changes secondary to changes in blood flow and deoxyhemoglobin in tumors. Deoxyhemoglobin acts as an endogenous paramagnetic MRI contrast agent by reducing apparent transverse relaxation time ( $R2^*$ , in  $\text{sec}^{-1}$ ) of neighboring tissues. BOLD MRI technique detects these relative changes in  $R2^*$ . In various murine cancer models, significant changes in tumor  $R2^*$  were demonstrated when altering concentrations of  $O_2$  administration. Rhee et al demonstrated an increase in  $R2^*$  values after HCC embolization in rabbits.

DCE-MRI has been used to study tumor pathophysiology and to follow antiangiogenic treatments. With the proposed concept of perfusion “normalization” with antiangiogenic therapy, a decrease in perfusion and blood volume is expected in tumors, however data on DCE-MRI in HCC treated with systemic

	Protocol Name:	Evaluation of HCC Response to Systemic Therapy with Quantitative MRI
	Principal Investigator:	[name]
	Primary Contact Name/Contact Info:	[name] [contact] [contact]
	Date Revised:	6/30/2017
	Study Number:	GCO12-0214

therapy is extremely limited. A recent perfusion CT paper showed that high pre-treatment MTT (mean transit time) and Ktrans were predictive of better response of HCC to bevacizumab and chemotherapy. MRE can be implemented on a standard MR system by installing a device for generating mechanical vibration in the liver under MR scanner control, a special MRE pulse sequence, and processing software to generate the diagnostic MRE images (elastograms). Several studies have demonstrated that MRE is an accurate method for diagnosing liver fibrosis, with liver stiffness increasing systematically with fibrosis stage. There is limited data on the use of MRE in focal liver lesions. This study showed that HCC and cholangiocarcinoma had significantly greater stiffness than fibrotic liver, benign tumors, and normal liver parenchyma.

FDG-PET has been used to probe HCC tumor grade, with increased uptake demonstrated in patients with high-grade HCC (102, 103). A correlation between FDG uptake and the number, size and stage of tumors as well as portal vein invasion has been demonstrated (104-108), suggesting that FDG-PET can identify more aggressive HCC tumor phenotypes. It is now possible to combine functional information from MRI and PET by using a whole body hybrid PET-MRI system (109, 110), which may maximize information on tumor aggressiveness, which may be in turn used for individualizing therapy (111). In this regard, PET-MRI systems may be instrumental for risk stratifying patients, and could be used as a preoperative tool for estimating the post-surgical risk of HCC tumor recurrence

The validation of new imaging criteria for prediction and assessment of early response to systemic therapy or to locoregional therapy with radioembolization will enable individualized therapy, such as patients not benefiting from these therapies may be proposed alternate therapies currently being developed.

### 3) Setting of the Human Research

The study will be conducted at the outpatient Radiology practice located in the Faculty Practice Associates (FPA) building or in the Center for Science and Medicine in the Hess Tower at Mount Sinai Medical Center. 1.5T and/or 3T FDA approved MRI systems (Siemens or GE) and/or a 3T mMR (hybrid PET/MR, Siemens) and ARFI ultrasound (Acuson S3000, Siemens) will be used for the study purpose.

### 4) Resources Available to Conduct the Human Research

Our MR research group has been actively investigating cutting edge MRI techniques for evaluation of focal and diffuse liver diseases. There is a large recruitment of patients with HCC at the Tisch Cancer Institute located at Mount Sinai School of Medicine (MSSM), and the Mount Sinai Medical Center (MSMC). Recruitment sources are from the Surgical Oncology group who performs approximately 100 resections for HCC annually, the Liver Transplant group (who performs approximately 100 adult liver transplants a year, including 40 for HCC), and the Hepatology group. The liver cancer program at Mount Sinai is structured as a multidisciplinary group including hepatologists, surgeons, oncologists, pathologists, radiologists, molecular biologists and epidemiologists. For this proposal, we expect to recruit 141 subjects over a 5-year period, including patients who will undergo liver resection referred

	Protocol Name:	Evaluation of HCC Response to Systemic Therapy with Quantitative MRI
	Principal Investigator:	[name]
	Primary Contact Name/Contact Info:	[name] [contact] [contact]
	Date Revised:	6/30/2017
	Study Number:	GCO12-0214

from Surgical Oncology group, and patients with unresectable HCC referred from Hepatology and Oncology services.

All personnel assisting with the research study are adequately informed about the protocol and their related duties and functions. The PI is an active member of the liver cancer program at Mount Sinai and has an open dialogue with all experts involved. Many members of the current research team already worked together in related projects and have experience and qualifications to conduct this research. All personnel supporting the project are trained according to IRB requirements. Their CVs/Biosketches to prove qualification are attached with this submission.

## 5) Study Design

### a) Recruitment Methods

Subjects with HCC will be identified and recruited for the study by their treating physicians at Surgical Oncology, Liver Transplant and Hepatology. The selection will be recommended by the physicians, who are familiar with their patient's history. The referring physicians will be considered significant contributors to the project.

The treating physician will be providing potentially eligible subjects with study information in form of a flyer and the consent form of the study. Subjects can take the information home and can think about the study and potential participation. The subject will be given the opportunity to contact the Research Coordinator to discuss the study details and to answer all questions about it. Also the Research Coordinator will be on hand to speak with a potential participant after they met with their treating physician.

For all referred interested subjects the Research Coordinator will review their medical records to check for their eligibility according to the inclusion/exclusion criteria and contraindications for MRI. We ensure by reviewing data from medical records that the subject population being asked to participate would be eligible to do so and that their safety during the study would not be at risk. A waiver of authorization to release PHI for research purposes has been requested.

Healthy volunteers will be recruited for the study by word-to-mouth recommendation and later on by MSSM broadcast emails. The study specific announcement will then be submitted to the IRB. Interested volunteers are asked to contact the Research Coordinator, who will check for contraindications in a dialogue with the potential subject.

### b) Inclusion and Exclusion Criteria

#### Inclusion criteria

##### Study group

1. Patients diagnosed with HCC, who will undergo resection or transplantation within 6 months, as part of routine clinical care and patients diagnosed with unresectable HCC.

	Protocol Name:	Evaluation of HCC Response to Systemic Therapy with Quantitative MRI
	Principal Investigator:	[name]
	Primary Contact Name/Contact Info:	[name] [contact] [contact]
	Date Revised:	6/30/2017
	Study Number:	GCO12-0214

2. Patients with unresectable HCC undergoing systemic therapy based on clinical indication or approved drug trial; and/or undergoing clinically indicated Y90 radioembolization.
3. 18 years of age and older.
4. Patient is able to give informed consent for this study.

**Control group**

1. Healthy volunteers 18 years of age and older.
2. Subject is able to give informed consent for this study.

**Exclusion criteria**

1. Age less than 18 years.
2. Unable or unwilling to give informed consent.
3. Contra-indications to MRI and/or PET/MRI
  - a. Electrical implants such as cardiac pacemakers or perfusion pumps
  - b. Ferromagnetic implants such as aneurysm clips, surgical clips, prostheses, artificial hearts, valves with steel parts, metal fragments, shrapnel, tattoos near the eye, or steel implants
  - c. Ferromagnetic objects such as jewelry or metal clips in clothing
  - d. Pregnant subjects
  - e. Pre-existing medical conditions including a likelihood of developing seizures or claustrophobic reactions.

Patients with GFR <30 will not undergo DCE-MRI with Gadolinium contrast. For patients with GFR < 30, we will still consider enrolling patients for a non-contrast MR protocol, including non-contrast sequences (DWI, BOLD and MRE). Patients with severe COPD will not undergo oxygen-enhanced sequences, due to risk of respiratory decompensation. Patients with uncontrolled diabetes will not undergo the PET/MRI study. Uncontrolled Diabetes” will be defined by high blood levels of glucose observed over 200 mg/dl secondary to untreated diabetes or to incompletely treated diabetes.

As with all patients referred for MRI and PET/MRI, each patient is screened for possible contraindications with a routine questionnaire.

**c) Number of Subjects**

150

**d) Study Timelines**

Duration of the study is 3 Years.

All subjects will undergo 1 to 2 MRI exams and ARFI.

We would like to ask a subset of 23 additional patients out of 150 if they are willing to undergo a PET/MRI study and ARFI.

We propose to assess response of therapy in a subset of 30 patients with unresectable HCC. These patients will be selected when they undergo treatment with systemic therapy such as sorafenib

	Protocol Name:	Evaluation of HCC Response to Systemic Therapy with Quantitative MRI
	Principal Investigator:	[name]
	Primary Contact Name/Contact Info:	[name] [contact] [contact]
	Date Revised:	6/30/2017
	Study Number:	GCO12-0214

(indicated clinically) or immunotherapy (using nivolumab) and/or radioembolization (indicated clinically). These patients will be imaged before treatment and 2-4 weeks after initiating therapy. Imaging will involve MRI only.

The total examination time per visit including the setup and routine MRI/ARFI/PET/MRI will be approximately 60-90 minutes.

#### e) Endpoints

- *Tumor response*: defined as the % of tumor necrosis diagnosed on image subtraction on subsequent routine clinically indicated MRI performed 3-6 months after initiating therapy.
- *Time to tumor progression*: defined as the time from initiating therapy to disease progression according to mRECIST criteria as diagnosed on follow-up routine contrast-enhanced MRI. Progression will be defined as an increase of at least 20% in the sum of the diameters of viable target lesions, taking as reference the smallest sum of the diameters of viable target lesions recorded since initiation of therapy.
- *Overall survival*: defined as the time from initiating therapy to death.

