#### f) Procedures Involved in the Human Research

All subjects will undergo 1 to 2 MRI exams and ARFI. During each visit, we will obtain the following MR parameters (DWI, BOLD, MRE and DCE-MRI). Patients referred for MR evaluation of the abdomen will receive all conventional MRI necessary to address the referral indication in addition to DWI, DCE-MRI, BOLD and MRE.

23 patients will be asked to undergo a single PET/MRI and ARFI study. These patients will not be asked to come back for a second PET/MRI study.

We will perform an independent prospective study in up to 30 additional patients with advanced HCC treated with sorafenib or nivolumab and/or Y90 to assess the role of pre-treatment and early changes in quantitative MR parameters for predicting tumor response, time to tumor progression and overall survival.

**Diffusion-weighted MRI (DWI)** will be performed using multiple single shot Echo Planar Imaging (EPI) or segmented EPI acquisitions or non EPI sequences with selected varied parameters and gradients. Diffusion parameters will be calculated (ADC: apparent diffusion coefficient, D: true diffusion coefficient, PF: perfusion fraction).

**BOLD MRI**: Before contrast injection, we will use a breath-hold multiecho T2\* sequence covering the whole liver under room air and after 20 min. of administration of pure O2 (10 L/min) and/or carbogen (95% oxygen and 5% carbon dioxide) through a facial mask or a cannula.

**MR Elastography**: Will be performed before contrast injection. The subject/patient will be asked to perform multiple breath-holds during the image acquisition.

**DCE-MRI** will be performed prior and after intravenous administration of Gadolinium chelates using a 2D or 3D fast T1-weighted sequence. An FDA approved gadolinium contrast agent will be administered. These include extra-cellular agents such as Gd-BOPTA (Multihance), a liver specific

	Protocol Name:	Evaluation of HCC Response to Systemic Therapy with Quantitative MRI
	Principal Investigator:	[name]
	Primary Contact Name/Contact Info:	[name] [contact] [contact]
	Date Revised:	6/30/2017
	Study Number:	GCO12-0214

agent such as Gd-EOB-DTPA (Eovist), and a blood-pool agent (gadofovesettrisodium, Ablavar). As the contrast is circulating through the body the patient will be imaged for approximately 5 minutes after contrast injection. The patient will hold his/her breath for as long as possible.

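### Tumor response is the absolute % necrosis on one follow-up MRI with no pre-treatment reference, so necrosis already present at entry counts as response and can distort the marker-response analysis

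*Combined protocol and SAP*

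**What the plan says.** Section 5e (Endpoints) says tumor response is "defined as the % of tumor necrosis diagnosed on image subtraction on subsequent routine clinically indicated MRI performed 3-6 months after initiating therapy". It names no baseline reading, change score or viable-tumor denominator. The next bullet, on time to progression, does name a reference: "taking as reference the smallest sum of the diameters of viable target lesions recorded since initiation of therapy".

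Section 5f (Procedures) describes a study in up to 30 additional patients with advanced HCC to "assess the role of pre-treatment and early changes in quantitative MR parameters for predicting tumor response", as well as time to progression and overall survival. Section 5d (Study Timelines) says "These patients will be imaged before treatment and 2-4 weeks after initiating therapy". Section 5f also says DCE-MRI "will be performed prior and after intravenous administration of Gadolinium chelates". A contrast-enhanced pre-treatment scan is therefore planned, but nothing links it to the response endpoint.

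The criteria in section 5b do not exclude earlier locoregional treatment. The Background calls chemoembolization "an effective therapy to cause tumor necrosis".

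**The concern.** Two things follow from the definition.

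First, the score mixes necrosis caused by study therapy with necrosis that was there before. That follows directly from the wording and needs no further assumption.

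Second, some predictors may share the same contaminant. The Background says "ADC measured with DWI has been shown to correlate negatively with tumor cellularity in brain, breast and prostate tumors" and that "effective tumor treatment results in a rise in tumor ADC". DCE-MRI measures contrast uptake, and a subtraction reading of necrosis also depends on enhancement. If the regions measured for ADC or perfusion include necrotic tissue, old necrosis could sit in both marker and outcome. A marker could then look predictive without carrying information about treatment effect. The reverse can also happen. The Background cites a perfusion CT study in which high pre-treatment Ktrans went with better response. Old necrosis would tend to lower perfusion and raise the follow-up necrosis score, which would weaken an association of that kind.

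The Background hopes that validated criteria will point patients who do not benefit toward alternate therapies, so an error in either direction matters.

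**Working it through.** **Direct arithmetic from the definition.** Let N0 be % necrosis before therapy and N1 the % at 3-6 months. The endpoint is N1.

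- Tumor 1: N0 = 40, therapy adds 0, so N1 = 40.
- Tumor 2: N0 = 0, therapy adds 30, so N1 = 30.

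The tumor on which therapy did nothing gets the higher response score.

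**Inputs for the size.** From the documents: 30 patients in the response cohort. The plan gives no figure to reproduce, because the supplied text states no test, alpha, effect size or necrosis distribution for this cohort. Everything else below is assumed.

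**Approximate formula.** Suppose N1 = N0 + T, with T the necrosis caused by therapy. A marker has correlation ρ with N0 and none with T. Then

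corr(marker, N1) = ρ · SD(N0) / √(SD(N0)² + SD(T)²).

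With ρ = 0.5 and SD(T) = 25 points:

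- SD(N0) = 10: 0.5 × 10 / √(100 + 625) = 5 / 26.9 = 0.19. Simulated false-positive rate at n = 30 (two-sided 5% Pearson test): 16%.
- SD(N0) = 20: 0.5 × 20 / √(400 + 625) = 10 / 32.0 = 0.31. False-positive rate: 40%.

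Widening the treatment effect to SD(T) = 35 with SD(N0) = 20 gives 10 / √(400 + 1225) = 10 / 40.3 = 0.25, so the spurious correlation shrinks. For scale, 30 patients give 80% power for a correlation of about 0.49.

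**Simulation on the bounded scale.** n = 30, two-sided 5% Spearman test, reading error SD 5 points on each scan, marker unrelated to treatment effect, marker-N0 correlation 0.3 to 0.7. Two effect forms were used: N1 = N0 + (1 − N0)K, where K is the share of viable tumor lost; and N1 = min(100%, N0 + D), where D is a fixed number of points added. The narrower rows use both forms (K mean 30, SD 15 or 25; D mean 25, SD 10 or 20). The wider rows use the first.

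| False-positive rate, % | N0 mean/SD 5/5 | 15/15 | 30/25 |
|---|---|---|---|
| Unadjusted, narrower treatment effect (SD 10-25) | 6-24 | 10-78 | 18-96 |
| Unadjusted, K mean/SD 40/35 | 5-6 | 7-17 | 11-40 |
| Unadjusted, K mean/SD 50/38 | 5-6 | 6-10 | 8-24 |
| Adjusted for N0 (partial Spearman), narrower effect | 5-13 | 5-15 | 5-11 |

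Adjusted rates under the wider treatment effects are no higher than those in the last row. The highest unadjusted rates need a marker-N0 correlation of 0.7 and the fixed-points form with SD 10.

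**Attenuation.** First form, K SD 15 or 25, marker correlated 0.5 with K and −0.5 with N0. Power in the right direction at N0 5/5, 15/15 and 30/25 is 47-59%, 7-21% and 0.3-3% unadjusted, against 60-69%, 52-67% and 47-64% adjusted. The loss is modest in the first case and severe in the last.

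**The case against.** The strongest case against runs as follows.

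- **The marker link is not in the documents.** A reader might infer that old necrosis determines the baseline markers. The Background ties ADC to cellularity in brain, breast and prostate tumors, not to necrosis in HCC, and no section says which regions are measured. If necrotic areas are left out, the link weakens. This stands: the link is a reasonable inference only.
- **Prevalence of old necrosis is unknown.** Eligibility is silent on prior treatment, and silence is not evidence of frequency. A reader might point to the inclusion of Y90, but here Y90 is a study treatment with imaging before and after, so necrosis it then causes is response. This also stands. If nearly all tumors are viable at entry, the problem is small.
- **The alarming rates are conditional.** A reader might take 80-95% as the expected error. Those figures assume an unadjusted test that the plan does not name and a fairly uniform treatment effect. A cohort pooling sorafenib, nivolumab and Y90 may well vary more, and then the ceiling is about 40%. Nor do the figures show that true effects would vanish: in the mildest case power falls only from 60-69% to 47-59%.
- **Image subtraction could mean subtracting the pre-treatment scan.** The wording places it on the later routine MRI, which points to subtraction within that examination. If the other sense was intended, the text should say so.
- **The text may have changed.** The 2018 modification form describes no change to this definition, but the revised endpoint text was not supplied.

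None of this supplies a baseline reference for the response score.

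**Conclusion.** The concern holds in a limited form and should be fixed. As written, response includes necrosis that predates therapy, and nothing in the eligibility criteria keeps such tumors out. That much is certain from the text.

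Distortion of the marker-response analysis is possible rather than shown. It depends on three things the documents do not give: how much necrosis patients have at entry, how strongly the markers track it, and how widely treatment effect varies. Under the assumptions above, the unadjusted false-positive rate runs from about 5% up to about 40% with a treatment-effect SD of 35-38 points. It reaches 80-95% only when substantial baseline necrosis and a strong marker link meet a narrower effect. Adjustment brings it to about 5-15%.

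The point concerns tumor response only. Time to progression and overall survival are defined separately and do not inherit it.

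**What to change.** 1. Read % necrosis on the planned pre-treatment contrast MRI, using a subtraction method matched as closely as possible to the follow-up reading. State that the subtraction is within each examination, if that is what is meant.
2. Make the main marker-response analysis adjusted for pre-treatment necrosis: a partial rank correlation, or follow-up necrosis regressed on marker plus pre-treatment necrosis. Specify it before outcomes are examined.
3. Report simple change and share of initially viable tumor lost as secondary. Neither is safe alone: in the simulations, false positives reached 45% for simple change and 58% for share lost when the treatment effect took the other form.
4. Record earlier locoregional treatment of each target lesion.
5. State whether the regions measured for the MR markers include necrotic tissue.

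**Cost.** One extra reading per patient, with no new scans or patients. Patients on the non-contrast protocol (GFR below 30) will have no baseline subtraction from the study scan. Study DCE-MRI and routine follow-up MRI may differ in sequence or contrast agent, so the two readings may not match fully. Reading error leaves some inflation: up to 15% in the main scenarios, and 33% against 59% unadjusted in an extreme case where therapy does nothing and reading error equals the baseline spread. Where the marker is unrelated to baseline necrosis, adjustment costs about 1 point of power if baseline necrosis is minimal and gains 6-27 points in the other scenarios.
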